#### **Hepatic Impairment**

After a single oral dose of posaconazole oral suspension 400 mg, the mean AUC was 43%, 27%, and 21% higher in subjects with mild (Child-Pugh Class A, N=6), moderate (Child-Pugh Class B, N=6), or severe (Child-Pugh Class C, N=6) hepatic impairment, respectively, compared to subjects with normal hepatic function (N=18). Compared to subjects with normal

hepatic function, the mean  $C_{max}$  was 1% higher, 40% higher, and 34% lower in subjects with mild, moderate, or severe hepatic impairment, respectively. The mean apparent oral clearance (CL/F) was reduced by 18%, 36%, and 28% in subjects with mild, moderate, or severe hepatic impairment, respectively, compared to subjects with normal hepatic function. The elimination half-life ( $t_{1/2}$ ) was 27 hours, 39 hours, 27 hours, and 43 hours in subjects with normal hepatic function and mild, moderate, or severe hepatic impairment, respectively. It is recommended that no dose adjustment of Noxafil is needed in patients with mild to severe hepatic impairment (Child-Pugh Class A, B, or C). Similar recommendations apply to posaconazole delayed-release tablets; however, a specific study has not been conducted with the delayed-release tablets.

## OVERDOSAGE

There is no experience with overdosage of posaconazole injection and delayed-release tablets. During the clinical trials, some patients received posaconazole oral suspension up to 1600 mg/day with no adverse reactions noted that were different from the lower doses. In addition, accidental overdose was noted in one patient who took 1200 mg BID posaconazole oral suspension for 3 days. No related adverse reactions were noted by the investigator. Posaconazole is not removed by hemodialysis.

## 2.3 Clinical Data to Date

### 2.3.1 Safety data from placebo-controlled trials of oral delayed-release tablets

The safety of posaconazole delayed-release tablets has been assessed in 230 patients in clinical trials. Patients were enrolled in a non-comparative pharmacokinetic and safety trial of posaconazole delayed-release tablets when given as antifungal prophylaxis (Delayed-Release Tablet Study 1). Patients were immunocompromised with underlying conditions including hematological malignancy, neutropenia post-chemotherapy, GVHD, and post HSCT. This patient population was 62% male, had a mean age of 51 years (range 19-78 years, 17% of patients were  $\geq 65$  years of age), and were 93% white and 16% Hispanic. Posaconazole therapy was given for a median duration of 28 days. Twenty patients received 200 mg daily dose and 210 patients received 300 mg daily dose (following twice daily dosing on Day 1 in each cohort). Table below presents treatment-emergent adverse reactions observed in patients treated with 300 mg daily dose at an incidence of  $\geq 10\%$  in posaconazole delayed-release tablet study. The most frequently reported adverse reactions ( $>25\%$ ) with posaconazole delayed-release tablets 300 mg once daily were diarrhea, pyrexia, and nausea. The most common adverse reaction leading to discontinuation of posaconazole delayed-release tablets 300 mg once daily was nausea (2%).

**Table: Posaconazole Delayed-Release Tablet Study 1: Number (%) of Subjects Treated with 300 mg Daily Dose Reporting Treatment-Emergent Adverse Reactions: Frequency of at Least 10%**

| Subjects reporting any Adverse Reaction | Posaconazole delayed-release tablet (300 mg)
(n=210) |      |
|---|---|------|
|   | 201   | (99) |
| Anemia                                  | 22  | (10) |
| Thrombocytopenia                        | 29  | (14) |
| Abdominal Pain                          | 23  | (11) |
| Constipation                            | 20  | (10) |
| Diarrhea                                | 61  | (29) |
| Nausea                                  | 56  | (27) |
| Vomiting                                | 28  | (13) |

CONFIDENTIAL

This material is the property of Cedars-Sinai Medical Center.

|                      |    |      |
|----------------------|----|------|
| Asthenia             | 20 | (10) |
| Chills               | 22 | (10) |
| Mucosal inflammation | 29 | (14) |
| Edema Peripheral     | 33 | (16) |
| Pyrexia              | 59 | (28) |
| Hypokalemia          | 46 | (22) |
| Hypomagnesemia       | 20 | (10) |
| Headache             | 30 | (14) |
| Rash                 | 34 | (16) |
| Hypertension         | 23 | (11) |

### CONTRAINDICATIONS

**Hypersensitivity:** Posaconazole is contraindicated in persons with known hypersensitivity to posaconazole or other azole antifungal agents.

**QT Prolongation with Concomitant Use with CYP3A4 Substrates:** Posaconazole is contraindicated with CYP3A4 substrates that prolong the QT interval. Concomitant administration of posaconazole with substrates pimozide and quinidine may result in increased plasma concentrations of these drugs, leading to QTc prolongation and torsades de pointes.

**Coadministration with the HMG-CoA Reductase Inhibitors Primarily Metabolized Through CYP3A4:** HMG-CoA reductase inhibitors (e.g., atorvastatin, lovastatin, and simvastatin) are contraindicated due to increased plasma concentration of these drugs can lead to rhabdomyolysis.

**Ergot Alkaloids:** Posaconazole may increase the plasma concentrations of ergot alkaloids (ergotamine and dihydroergotamine) which may lead to ergotism.

### 2.4 Dose Rationale

Noxafil® delayed-release tablets are available as yellow, coated, oblong tablets, debossed with "100" on one side containing 100 mg of posaconazole. Noxafil® delayed-release tablets are approved for prophylaxis of invasive aspergillus and Candida infection at a dose of 300mg (3 tablets) twice a day on the first day (loading dose) followed by 300mg (3 tablets) once a day, starting on the second day (maintenance dose). At this dose, steady state parameters are as noted in Table 1. The current trial will evaluate the effects of this FDA-approved dose (for fungal prophylaxis) in patients with Crohn's disease demonstrating genetic susceptibility to fungal infection. We propose a 3 month treatment duration which is expected to have inhibitory effects on the intestinal fungome (specifically *Malassezia* spp) as well as clinical effects on inflammation, as evidenced by a case series demonstrating clinical benefit for 5 patients with Crohn's disease after itraconazole therapy was incidentally prescribed for fungal infections.

## 3 Study Objectives

### Primary Objective

- To assess the effects of posaconazole endoscopic disease activity at week 12 in patients with active Crohn's disease

### Secondary Objectives

- To assess the preliminary efficacy of posaconazole for the induction of clinical remission in patients with active Crohn's disease with genetically-determined CARD9 S12N risk allele

- To assess the preliminary safety and tolerability of posaconazole for the induction of clinical remission and endoscopic response in patients with active Crohn's disease with genetically-determined CARD9 S12N risk allele
- To assess the preliminary influence on quality-of-life of posaconazole in patients with active Crohn's disease with genetically-determined CARD9 S12N risk allele
- To assess the pharmacokinetics (PK) of posaconazole in patients with active Crohn's disease with genetically-determined CARD9 S12N risk allele
- To assess changes in the intestinal microbiota after treatment with posaconazole in patients with active Crohn's disease with genetically-determined CARD9 S12N risk allele
- To determine changes in gene expression (transcriptomics) in colonic mucosa after posaconazole in patients with active Crohn's disease with genetically-determined CARD9 S12N risk allele

## 4 Study Design

[figure not shown]
### 4.1 General Design

This study is designed as a two-center, placebo-controlled induction trial in 24 subjects with active Crohn's disease, who demonstrate at least one CARD9 S12N risk allele. Expected duration of participation is forty weeks. This will include screening period up to four-weeks and a twelve-week, double-blind induction period.

- Subjects who complete the 12-week induction period, meet criteria for active disease, AND upon unblinding at 12 weeks are determined to have received placebo during the 12-week induction period will be eligible to receive open-label posaconazole for 12 weeks, followed by a 12-week follow-up period.
- Subjects who complete the 12-week induction period and do not meet criteria for active disease, OR upon unblinding at 12 weeks are determined to have received posaconazole during the 12-week induction period will have a follow-up period of twenty-four weeks.

Clinical remission will be defined as the proportion of subjects with endoscopic improvement, defined by a decrease in 50% of the SES-CD endoscopic score. Subjects experiencing early withdrawal from study will be scheduled for a safety follow-up visit four weeks after the date of withdrawal.

**Figure 1: Study Design**

CONFIDENTIAL

This material is the property of Cedars-Sinai Medical Center.

## **4.2 Primary Study Endpoints**

The primary endpoint is the proportion of subjects in endoscopic response at week 12, defined by SES-CD reduction of >50% from baseline.

## **4.4 Primary Safety Endpoints**

- Incidence and severity of adverse events
- Change from baseline of laboratory values (chemistry, hematology, electrolytes, liver enzymes, renal function)
- Incidence of electrocardiogram (EKG) abnormalities including QTc prolongation

## **4.5 Quality-of-life Endpoints**

- Inflammatory bowel disease questionnaire (IBDQ)
- Short Form SF-36 (SF-36)

## **4.6 Pharmacokinetics Endpoints**

- Serum posaconazole concentrations at weeks 2, 4, 6, 8, 10, and 12. Relationship between posaconazole serum concentration and clinical and antifungal effects

## **4.7 Transcriptomics Endpoints**

- Changes in stool and mucosal washing metabolites
- Changes in microbiome / metabolome reflected in gene expression patterns in mucosal biopsies

# **5 Subject Selection and Withdrawal**

Subjects (n=24) will be individuals with active Crohn's disease (SES-CD  $\geq 6$  AND PRO2 score of abdominal pain  $\geq 2$  OR PRO2 daily stool frequency  $\geq 4$ ) despite use of conventional therapy. Subjects will be randomly assigned to receive posaconazole or placebo in 1:1 fashion. In this 40-week trial, subjects assigned to treatment will be administered posaconazole (Noxifil®, Merck) 300mg daily for 12 weeks. and then observed off posaconazole over the next 24 weeks. In addition to the treatment intervention, subjects also will provide samples for parallel translational studies including blood for genetic analysis, stool samples for biomarker and microbial composition analysis, and biopsies for mucosal gene expression analysis. Patients meeting criteria for active disease at 12 weeks will be offered open-label posaconazole for 12 weeks and will continue all study-related visits and procedures until final safety visit at week 36.

## **5.1 Randomization**

At the baseline visit, subjects will be randomized via REDCap to receive posaconazole or placebo.

## 5.2 Inclusion Criteria

1. Male or female patients  $\geq 18$  years of age.
2. A diagnosis of CD with minimum disease duration of 6 months with involvement of the ileum and/or colon documented on colonoscopy
3. Have an endoscopically-confirmed active Crohn's disease with active disease defined by SES-CD  $\geq 6$  ( $\geq 4$  if ileal only), AND active symptoms of Crohn's disease (CDAI  $>220$ )
4. Subjects receiving oral aminosalicylates (at a stable dose for 2 weeks prior to baseline), immunomodulators (at a stable dose for 4 weeks prior to baseline), anti-TNF, anti IL12/23, or anti-integrin therapy (at stable maintenance doses for  $\geq 8$  weeks) may continue their use during the study.
5. Subjects receiving oral corticosteroids may continue their use during the study provided the dose (prednisone up to 20 mg/day, budesonide up to 9 mg/day) has been stable for two weeks prior to screening.
6. Lab findings of hypokalemia, hypomagnesemia, or hypocalcemia are eligible, provided electrolyte abnormalities are corrected and stable prior to study enrollment.
7. Have had age-appropriate and disease-duration-appropriate colon cancer screening without unresected dysplasia.
8. Women of childbearing age, excluding those with prior bilateral tubal ligation or at least one-year post-menopause, must not be pregnant, lactating, or planning to become pregnant. They must agree to use effective contraception throughout the study period.
  - a. Option 1: Any one of the following highly effective methods: hormonal contraception for example, birth control pills, injection, implant, transdermal patch, vaginal ring); intrauterine device (IUD); tubal ligation (tying your tubes); or a partner with a vasectomy
  - b. Option 2: Any two of the following effective methods: male or female condom PLUS one of the following additional barrier methods (a)diaphragm with spermicide; (b) cervical cap with spermicide; or (c) contraceptive sponge with spermicide
9. Subjects must be able to provide informed consent and understand, agree with, and be able to adhere to daily diary entries, all scheduled visits, tests, procedures, and protocol in English.

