## Metabolism

Posaconazole primarily circulates as the parent compound in plasma. Of the circulating metabolites, the majority are glucuronide conjugates formed via UDP glucuronidation (phase 2 enzymes). Posaconazole does not have any major circulating oxidative (CYP450 mediated) metabolites. The excreted metabolites in urine and feces account for ~17% of the administered radiolabeled dose. Posaconazole is primarily metabolized via UDP glucuronidation (phase 2 enzymes) and is a substrate for p-glycoprotein (P-gp) efflux. Therefore, inhibitors or inducers of these clearance pathways may affect posaconazole plasma concentrations.

*In vitro* studies with human hepatic microsomes and clinical studies indicate that posaconazole is an inhibitor primarily of CYP3A4. A clinical study in healthy volunteers also indicates that posaconazole is a strong CYP3A4 inhibitor as evidenced by a >5-fold increase in midazolam AUC. Therefore, plasma concentrations of drugs predominantly metabolized by CYP3A4 may be increased by posaconazole. For this reason, the following drugs studied clinically, for which plasma concentrations were affected by posaconazole, will be prohibited during the current proposed trial (cyclosporine, tacrolimus, sirolimus, simvastatin, midazolam, rifabutin, phenytoin, ritonavir, atazanavir [see *Exclusion Criteria*]).

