## 5.3 Exclusion Criteria

The presence of any of the following will exclude a subject from enrollment:

1. Known hypersensitivity or allergy to posaconazole or other azole antifungal agents
2. Concomitant medications primarily metabolized by CYP3A4 including (***but not limited to***):
  - a. HMG-CoA inhibitors primarily metabolized by CYP3A4 (increases risk of rhabdomyolysis)
  - b. Sirolimus
  - c. Ergot alkaloids
  - d. Vincristine
  - e. upadacitinib
3. Proarrhythmic conditions
4. Moderate or severe renal impairment (Cr Clearance  $<50$ )
5. Elevated transaminases or bilirubin  $> 2.5x$  ULN.
6. Current diagnosis of ulcerative colitis, indeterminate colitis, ischemic colitis, infectious colitis, or microscopic colitis.
7. Fulminant colitis, toxic megacolon, peritonitis, ileostomy or colostomy.

CONFIDENTIAL

This material is the property of Cedars-Sinai Medical Center.

8. Stool sample positive for pathogens including ova and parasites, *Salmonella*, *Shigella*, and *C. difficile* at screening.
9. History of any clinically significant neurological, renal, hepatic, gastrointestinal, pulmonary, metabolic, cardiovascular, psychiatric, endocrine, hematological disorder or disease or any other medical condition that, in the Investigators opinion, would prevent the subject from participation in the study.
10. Treatment with antibiotics, antifungal agents, probiotics, or prebiotics within two weeks of screening.
11. Alcohol or drug abuse (in the opinion of the Investigator) that would interfere with compliance.

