### **5.7 Open Label Posaconazole:**

At 12 weeks, subjects will undergo colonoscopy and clinical assessment for response, after which they will be unblinded. Subjects who meet criteria for active disease AND who are determined to have received placebo will be eligible to receive 12 weeks of open-label posaconazole. Eligibility Criteria for open label posaconazole:

1. Endoscopically-confirmed active Crohn's disease with active disease defined by SES-CD  $\geq 6$  ( $\geq 4$  if ileal only) based on local reading, AND
2. Active symptoms of Crohn's disease (CDAI  $>220$ ), AND
3. Received placebo during the 12-week induction period

Subjects who meet the above criteria and opt to receive open label posaconazole will be monitored for safety / adverse events at follow-up visits. Changes in corticosteroid dosing will be permitted after 12 weeks, regardless of whether subjects are receiving posaconazole or not. All subjects will undergo colonoscopy at 36 weeks.

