### **6.5 Prior and Concomitant Therapy**

The following concomitant therapies are allowed as long as a stable dose was administered per eligibility criteria:

- Biologic agents (infliximab, adalimumab, certolizumab, ustekinumab, vedolizumab)
- Immunomodulators (azathioprine/6-mercaptopurine)
- Oral 5-aminosalicylates or sulfasalazine

Oral corticosteroid preparations (maximum budesonide 9 mg/day, or prednisone 20 mg/day or equivalent) will be allowed as long as the dose has been stable dose for two weeks prior to screening. The dosage may not be reduced during the 12-week study period without premature discontinuation from the trial. Any dosage increases beyond that prescribed at the start of the trial will result in early withdrawal from study due to progression of Crohn's disease.

Concomitant prescribed therapies, non-prescription supplements, and herbal preparations which affect hepatic metabolism, antibiotics, probiotics, and antidiarrheals will not be allowed during the study. Drugs predominantly metabolized by CYP3A4 may be increased by posaconazole. Examples of drugs prohibited during the current proposed trial include, but are not limited to: cyclosporine, tacrolimus, sirolimus, simvastatin and other HMG-CoA inhibitors, midazolam, rifabutin, phenytoin, ritonavir, atazanavir, and upadacitinib.

Data regarding the composition, dosage, dosing schedule, route of administration, and initiation/end dates of therapy will be recorded for each concomitant therapy.

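### Oral budesonide is permitted by name although drugs mainly metabolised by CYP3A4 are excluded, so budesonide users on posaconazole may have raised steroid exposure in the 12 blinded weeks

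*Combined protocol and SAP*

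**What the plan says.** Budesonide is permitted by name and with a dose cap in three places. Inclusion 5, in the synopsis and again in Section 5.2, states: "Subjects receiving oral corticosteroids may continue their use during the study provided the dose (prednisone up to 20 mg/day, budesonide up to 9 mg/day". Section 6.5 agrees: "Oral corticosteroid preparations (maximum budesonide 9 mg/day, or prednisone 20 mg/day or equivalent) will be allowed". Both require a dose that has been stable for two weeks before screening.

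The CYP3A4 restrictions stand alongside. Exclusion 2 (synopsis and Section 5.3) begins "Concomitant medications primarily metabolized by CYP3A4 including" and gives a list that is expressly not exhaustive. Section 6.5 warns: "Drugs predominantly metabolized by CYP3A4 may be increased by posaconazole". It then introduces its list with "Examples of drugs prohibited during the current proposed trial include, but are not limited to". Budesonide is neither named nor exempted in either list. The reason for the restriction is in Section 2.2.2, Metabolism: "posaconazole is a strong CYP3A4 inhibitor as evidenced by a >5-fold increase in midazolam AUC".

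On the steroid dose, Section 6.5 says: "The dosage may not be reduced during the 12-week study period without premature discontinuation from the trial". An increase above the starting dose leads to withdrawal for disease progression. The restriction ends with the blinded period. Section 5.7 says: "Changes in corticosteroid dosing will be permitted after 12 weeks, regardless of whether subjects are receiving posaconazole or not".

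**The concern.** The plan treats CYP3A4 inhibition as serious enough to exclude a whole class of drugs, yet it admits by name a steroid that, on general pharmacology, belongs to that class. If exclusion 2 is applied literally, it turns away a patient whom inclusion 5 admits, and the two sites could decide differently about the same patient. If the named permission is followed, which is more likely in practice, budesonide users assigned to posaconazole meet a foreseeable interaction. Section 2.2.2 puts posaconazole steady state at Day 6, so the inhibition would last for most of the 12 weeks.

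The dose rule adds to this. Subjects and clinical staff are masked (Section 7.2). An investigator who suspects steroid excess cannot simply lower the budesonide dose and keep the subject in the trial. Placebo non-responders on budesonide would meet the same interaction if they took open-label posaconazole, but their steroid dose may then be changed. What is at stake is the safety of a few individuals and consistent application of the criteria.

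**Working it through.** **1. The plan's own figure.** Section 9.1 gives 76% power for 11 per arm, 10% versus 70% response, Fisher's exact test at 0.05. Full binomial enumeration of the two-sided test gives 75.5%, with an attained type I error of 0.0017 at a 10% rate in both arms (the plan states 0.002). Both figures reproduce. None of their inputs involves steroid use, so this point does not alter them.

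**2. The texts side by side.**

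| Step | Source | In the documents? |
|---|---|---|
| Posaconazole strongly inhibits CYP3A4 | Section 2.2.2 | Yes |
| Drugs mainly metabolised by CYP3A4 are excluded, open list | Exclusion 2 | Yes |
| Budesonide up to 9 mg/day is allowed | Inclusion 5, Section 6.5 | Yes |
| Budesonide is a deliberate exception | – | No such text |
| Budesonide is mainly a CYP3A4 substrate | General pharmacology | No; assumption |
| No steroid reduction in the 12 weeks without premature discontinuation | Section 6.5 | Yes |
| Single-subject waivers from the protocol are possible | Appendix 6 | Yes |

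Given the assumption in the fifth row, the second and third rows conflict, and the first and third together imply the interaction.

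**3. How many subjects.** Inputs: 24 subjects randomised 1:1 (Section 5), so 12 on posaconazole. The share s of budesonide users is not in the documents; 5%, 10% and 25% are assumed. Expected users on posaconazole = 12 × s. Chance of at least one = 1 − (1 − s)^12.

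| s | 12 × s | 1 − (1 − s)^12 |
|---|---|---|
| 5% | 0.6 | 1 − 0.95^12 = 46% |
| 10% | 1.2 | 1 − 0.90^12 = 72% |
| 25% | 3.0 | 1 − 0.75^12 = 97% |

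The chance passes one half at s of about 5.6%. These figures count exposed subjects. They do not measure harm, because the documents give no figure for the rise in budesonide exposure.

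**4. Recruitment cost of excluding budesonide.** Otherwise eligible candidates needed to enrol 24 = 24 / (1 − s): 24/0.95 = 25.3, 24/0.90 = 26.7 and 24/0.75 = 32.0, or 26, 27 and 32 after rounding up.

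**The case against.** The strongest objection is that the key link lies outside the documents. None of their lists of affected or barred drugs names budesonide, and without that link there is neither a conflict nor an interaction. This stands as a limit on confidence. It does not remove the point, because exclusion 2 is open-ended and no site can apply it to an unlisted drug without general knowledge of how that drug is metabolised. The premise is of that ordinary kind and is declared as an assumption.

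Second, a specific permission with a dose cap, repeated consistently, would normally govern over a general class exclusion. A compliance officer also checks all eligibility criteria at study entry (Appendix 6). This probably limits the eligibility confusion, but it means that budesonide users would be enrolled and exposed.

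Third, a reader might infer that the investigator has no choice but to continue the dose or remove the subject. The documents do not support that. Appendix 6 provides for single-subject waivers approved by the DSMB, and Section 10.1.1 contemplates an unreviewed protocol change to remove an apparent immediate hazard. Withdrawal for safety (Section 5.6.1), with a safety visit four weeks later and follow-up of adverse events (Section 5.6.2), is itself a proper response. Fixing the steroid dose also protects the week 12 endpoint from steroid changes.

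Fourth, general safeguards are substantial: vital signs, weight, examination, chemistry, lipids, adverse events and concomitant medication are reviewed every two weeks (Section 7.3, Table 1), and the DSMB sees unblinded data and can halt the trial (Appendix 6). All of this stands, though none of it directs anyone to this interaction.

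**Conclusion.** The point holds as a safety and eligibility-consistency issue that should be fixed, with medium confidence. It rests on the assumption that budesonide is mainly a CYP3A4 substrate. The exposure rise is of unknown size and few subjects would be affected, as the table of assumed usage shows. Even so, the risk to those subjects is foreseeable and avoidable. The restriction on dose reduction applies to the 12 blinded weeks only.

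A reader might go further and infer that a steroid effect confined to the posaconazole arm invalidates the comparison. The documents do not support that. Randomisation still gives a valid comparison of assigning posaconazole or placebo on top of background therapy, and any change in budesonide exposure is a consequence of that assignment. It could complicate attributing a benefit to the antifungal action, but neither the share of users nor the effect on response can be taken from the documents. As an illustration on assumed inputs only, suppose posaconazole has no effect of its own and raises response solely in budesonide users. With 20% users responding at 20% instead of 10%, the chance of a significant result is 0.3%. With 60% users responding at 50%, it is 11.5%. A range that depends wholly on assumptions cannot support a claim about the trial's result.

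**What to change.** Remove budesonide from the permitted corticosteroids in inclusion 5 (synopsis and Section 5.2) and Section 6.5. Add it to exclusion 2 (synopsis and Section 5.3) and to the prohibited drugs in Section 6.5. That last list applies throughout the trial, so it also covers open-label posaconazole. Prednisone could remain, but separating it from budesonide on CYP3A4 also rests on pharmacology outside the documents, which the sponsor should confirm.

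The cost is six wording edits, submission of an amendment to the IRB (Section 13), and a rule for any budesonide users already enrolled. No new visits or data are needed. On the assumed usage range, recruitment would need about two to eight more otherwise eligible candidates.

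If the sponsor intends to keep budesonide, three changes are needed together: name it as an explicit exception in exclusion 2 and Section 6.5; add a check for signs of steroid excess at the two-weekly visits; and allow its dose to be reduced for suspected steroid excess without premature discontinuation. Without the third change the dose restriction would remain.
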